A Phase 2 Trial of N-Acetylcysteine in Biliary Atresia after Kasai Portoenterostomy

Department of Pediatrics, Division of Gastroenterology, Hepatology, and Nutrition, Baylor College of Medicine and Texas Children's Hospital

Principal Investigator:	[name]., Ph.D. [contact] [name] E-mail: [contact]
Sub-investigators:	[name]. [name]. [name], BS
Collaborators:	[name]. [name]. [name], N.P. [name]. [name]. [name]. [name]. [name] [name].

Protocol No.	Date Changed	Reason for Change
V1.10	07/07/2023	Removed Sub-Investigator
V1.9	09/15/2021	Removed Sub-Investigator and
		Added Sub-Investigator
V 1.8	11/06/2020	Added clarification for subject
		replacement
V1.7	12/12/2019	Added Sub-Investigator
V1.6	06/28/2019	Added Sub-Investigator
V1.5	01/11/2019	Protocol Amendment
v1.4	7/21/17	Reflects changes to consent from
		BCM for Protocol H-40962
v1.3	7/19/17	Reflects changes from 6/30/17
		FDA call for IND #135796
v1.2	4/28/17	Reflects changes from 1 st DSMB
		meeting
v1.1	-	-

Biliary atresia (**BA**) is a devastating liver disease of infancy, characterized by bile duct obstruction leading to liver fibrosis, cirrhosis, and eventual need for transplantation in most cases. BA is treated with Kasai portoenterostomy (**KP**). KPs can achieve bile drainage and improve outcomes. However, even with standard evidence of "good bile flow," bile flow rarely normalizes completely and liver disease continues to progress.

In this study, we test whether intravenous N-acetylcysteine (NAC) can improve bile flow after KP. Our rationale is that NAC leads to synthesis of glutathione, which is a powerful stimulator of bile flow. Our primary objective is to determine whether NAC normalizes total serum bile acid (TSBA) concentrations within 24 weeks of KP. Achieving normal TSBAs is uncommon with current standard-of-care, and is predicted to be associated with better long-term outcomes. Our secondary objectives are to describe how other parameters commonly followed in BA change with NAC therapy, as well as report adverse events occurring with therapy and in the first two years of life. This study follows the "minimax" Phase 2 clinical trial design.

Table of Contents

Α.	Objectives 5								
В.	Background and Rationale								
C.	2. Enrollment Procedures								
	i.	Inclusion Criteria	6						
	ii.	Exclusion Criteria	6						
	iii.	Total Planned Enrollment	6						
	iv.	Inclusion of Women	6						
	v.	Inclusion of Minorities	6						
	vi.	Inclusion of Children	6						
D.	Stı	udy Implementation							
	i.	Study Design	6						
	ii.	Study Procedure	7						
	iii.	Consent Procedure	7						
	iv.	Drug Administration	7						
	v.	Observations	8						
	vi.	Dose Modifications	9						
	vii.	Concurrent Treatment	9						
	viii	. Removal of Patients from Study	10						
Е.	Da	ta Collection							
	i.	Clinical Data	10						
	ii.	Adverse Events	10						
F.	Sta	atistical Considerations							
	i.	Overview	10						
	ii.	Sample-Size Calculations	11						
G.	Etł	hical Issues							
	i.	Informed Consent	11						
	ii.	Children as Research Subjects	11						
Н.	Ph	armaceutical Information							
	i.	Formulation	11						

N-Acetv	Icvsteine in BA	
11,1001	ii. Storage	11
	iii. Administration	12
	iv. Toxicities	12
I.	References	13
J.	Appendix	
	i. Data and Safety Monitoring Plan	17
	ii. Data and Safety Monitoring Board Charter	23

N-Acetylcysteine in BA **A. Objectives**

- 1) To determine if N-acetylcysteine (NAC) therapy normalizes total serum bile acids (TSBAs) within 24 weeks after Kasai portoenterostomy (KP) for biliary atresia (BA) (primary outcome)
- 2) To describe changes in laboratory markers for disease progression in the first two years of life (secondary outcome)
- 3) To describe changes in weight in the first two years of life (secondary outcome)
- 4) To describe occurrence of sentinel events related to worsening liver disease (cholangitis, development of ascites, variceal bleed, liver transplant listing, liver transplant, death) in the first two years of life (secondary outcome)
- 5) To document adverse events which may be associated with NAC therapy (secondary outcome)

B. Background and Rationale

Biliary atresia (**BA**) is a disease characterized by fibro-obliteration of extrahepatic bile ducts leading to impaired bile flow.¹ BA is treated with the Kasai portoenterostomy (**KP**), an operation which connects the liver directly to the intestine in attempt to relieve bile back-up and promote bile flow. KPs have variable success. KPs occasionally normalize bile flow and stop disease progression.² More commonly, however, bile flow never completely normalizes after KP. This can be detected by elevated total bilirubin (**TB**) or conjugated bilirubin (**Bc**) serum concentrations, or, when TB and Bc are normal, elevated total serum bile acids (**TSBA**) concentrations.^{3–} Impaired flow leads to fibrosis, cirrhosis, and eventual need for liver transplantation. Given these uneven results, therapies are urgently needed to enhance the KP's success.

We hypothesize that N-acetylcysteine (**NAC**) will improve outcomes after KP, because NAC is a precursor for the powerful choleretic molecule glutathione.^{6–9} Our hypothesis assumes that better bile flow will lead to better outcomes. Two lines of evidence support this assumption. First, good bile flow correlates with slower disease progression in BA. For example, a recent study showed infants with good bile flow after KP were significantly less likely to develop failure-to-thrive, ascites, hypoalbuminemia, or coagulopathy in the first two years of life.³ Furthermore, these infants had significantly higher transplant-free survival in the same time period. In this study, TB <2.0 mg/dL within three months of KP was used as the marker for good bile flow.

Second, poor bile flow accelerates disease progression after KP. For example, poor bile flow stimulates bile duct proliferation through bile acid-induced TGR5 signaling.¹⁰ Proliferating bile ducts in turn may lead to two changes: (i) biliary cirrhosis, as fibrotic tissue is created around the new ducts; and (ii) further impaired flow, as bile must

travel through the convoluted proliferating ducts. In addition, poor bile flow prevents hepatocytes from properly localizing MRP2 (the Bc efflux transporter) and BSEP (the bile acid efflux transporter) to the canalicular membrane.^{11–13} As a result, Bc and bile acids accumulate in hepatocytes. Their intracellular concentrations eventually increase enough to drive their exit through basolateral membrane channels, which ultimately results in elevated Bc and TSBAs in the systemic circulation.

NAC has a number of properties that make it an especially attractive potential therapeutic agent. First, glutathione creates an osmotic gradient in the bile duct lumen which drives one-third of total bile flow in humans (the other drivers are bile acids and secretin/bicarbonate).^{7–9,14} Second, NAC is a Food and Drug Administration-approved therapy for another serious liver condition in neonates and children (acetaminophen overdose).¹⁵ It has also been used for other liver and non-liver indications in

Table: Other Studies Using IntravenousNAC in Neonates

Liver-related

- Parenteral nutrition associated cholestasis^{16,17}
- Nonacetaminophen acute liver failure^{18,19}
- Neonatal hemochromatosis (gestational alloimmune liver disease)²⁰
- Liver-unrelated
- Bronchopulmonary dysplasia²¹
- Chorioamnionitis^{22,23}

neonates, with few reported adverse events (Table).^{16–23} Third, glutathione is an anti-oxidant, which could

scavenge the free radicals contributing to cirrhosis. Fourth, glutathione is catalyzed into glycine, glutamate, and cysteine by gamma-glutamyl transferase (**GGT**), thereby potentially fulfilling a nutritive role for cholangiocytes.^{14,24,25} Preclinical studies are also promising, with glutathione's strong choleretic properties best established in rat flow studies and NAC's hepatoprotective effects documented in rescuing different mouse models of cholestasis.^{14,26–28}

To test our hypotheses, we will administer intravenous NAC continuously for seven days and determine the number of subjects with normal TSBAs (0-10 umol/L) within 24 weeks of KP. In addition, markers of BA progression, such as abnormal laboratory results, failure-to-thrive, and occurrence of complications related to chronic liver disease, will be described over the first two years of life. Finally, all adverse events occurring during NAC infusion and in the 21 days after its completion will be recorded. Our study employs the two-stage "minimax" Phase 2 clinical trial design, a design commonly used in oncological trials to determine whether a particularly therapy has sufficient activity to warrant a larger Phase 3 trial.²⁹ The two-stage "minimax" design offers two distinct advantages compared to other designs: (i) early termination if the drug is not efficacious; and (ii) small sample sizes, because historical controls rather than a separate control arm are used.

C. Enrollment Procedures

- i. Inclusion Criteria (all must be met)
 - a) Age less than or equal to 90 days at time of KP (standard age range in which KPs are performed)
 - b) BA diagnosis made by intraoperative cholangiography and KP performed at Texas Children's Hospital, Texas Medical Center Campus
 - c) Legal guardian(s) sign consent after understanding risks and investigational nature of study

ii. Exclusion Criteria

- a) Decompensated liver disease (INR >1.3) despite parenteral Vitamin K administration
- b) KP not performed for any reason (i.e., normal intraoperative cholangiography, or liver found to be too diseased intraoperatively to proceed with KP)
- c) Active respiratory infection
- d) Renal impairment, as defined by having an eGFR < 60 mL/min/1.73m² or creatinine clearance < 60 mL/min (https://www.niddk.nih.gov/health-information/communication-programs/nkdep/laboratoryevaluation/glomerular-filtration-rate-calculators/children-conventional-units)
- e) Presence of severe concurrent illnesses, such as pulmonary (i.e., bronchopulmonary dysplasia), neurological, cardiovascular, metabolic, endocrine, and renal disorders, which may be congenital or acquired, that would interfere with the conduct and results of the study
- **iii.** Total Planned Enrollment 12 subjects (minimum), 16 subjects (maximum); see below for discussion of sample size.
- iv. Inclusion of Women Male and female infants will be enrolled in this study. There may be more females than males enrolled, given that BA is slightly more common in females.
- v. Inclusion of Minorities Enrollment will be open to infants of all racial and ethnic backgrounds. Minority representation will reflect the racial/ethnic diversity of patients seen at the study hospital.
- vi. Inclusion of Children This trial will only enroll infants ≤90 days old.

D. Study Implementation

i. Study Design – This is an open label, Phase 2 study of seven days of intravenous NAC treatment after KP. Subjects will be followed for the first two years of life, and no additional clinic visits or testing beyond those routinely performed for routine BA clinical care at Texas Children's Hospital will be performed.

ii. Study Procedure

- a) Before KP
 - (1) Identify cholestatic infants likely to have BA who fulfill inclusion criteria
 - (2) Approach parent(s)/guardian(s) and explain study
- b) After KP until hospital discharge (typical length-of-stay 10-14 days)
 - (1) Consent parent(s)/guardian(s) and answer any remaining questions
 - (2) Initiate continuous intravenous NAC therapy (6.25 mg/kg/hour of 10 mg/ml solution, or 0.625 ml/kg/hour, to give 150 mg/kg/day) within 24 hours of completion of KP (initiation to occur in pediatric intensive care unit, where all patients are admitted for observation after KP)
 - (3) Continue therapy for a total of seven days
 - (4) Collect results from laboratory tests drawn as part of standard clinical care
 - (5) Monitor for adverse events (including serious adverse events)
- c) After hospital discharge until 28 days post-KP (1) Monitor for adverse events
- d) After hospital discharge until two years of life
 - (1) Collect laboratory test results and weights measured as part of standard clinical care
 - (2) Monitor for sentinel events related to progression of liver disease (cholangitis, development of ascites, variceal bleed, liver transplant listing, liver transplant, death)
 - (3) Monitor for serious adverse events
- **iii. Consent Procedures** Parent(s)/guardian(s) will be approached before intraoperative cholangiogram/KP, and hence before the BA diagnosis is definitively made (information given but no signatures no obtained). While the KP is being performed, the study team will obtain formal consent.

iv. Drug Administration

- a) Dosage:
 - NAC 150 mg/kg/day intravenous infusion run continuously over 24 hours (administered through dedicated intravenous line). If the IV has to be interrupted due to common expected events during IV treatment (e.g. IV leak, etc), interruption will be noted in the subject chart with stop/re-start time and reason but not considered a protocol deviation unless the interruption lasts longer than 30 minutes. Interruptions > 30 minutes will be considered a protocol deviation. Similar dosing was used in infants/children in at least five studies:
 - Pharmacokinetic study delivering 100 mg/kg/day NAC intravenously over 21-24 hours for 1 day immediately after birth in premature infants gestational age 24-31 weeks.³⁰ No adverse events associated with NAC treatment were reported.
 - Case series delivering 100 mg/kg/day NAC intravenously over 24 hours for multiple weeks in infants ages 0-3 weeks with neonatal hemochromatosis/gestational alloimmune liver disease.³¹ No adverse events associated with treatment were reported.
 - Case series delivering 70-135 mg/kg/day NAC intravenously over 12 hours for multiple months in children ages 4 months-13 years with TPN-dependent short bowel syndrome.¹⁷ No adverse events associated with NAC treatment were reported.
 - Retrospective review of administering 100 mg/kg/day NAC for 1-77 days (median 5 days) in children median age 3.51 years (range 0.005-17.4 years) with non-acetaminophen-induced acute liver failure.¹⁸ Three subjects had a rash (NAC therapy continued), two subjects had bradycardia (NAC therapy continued), one subject had tachycardia (NAC therapy continued), one subject had dizziness and peripheral edema (NAC dose reduced), and one child had bronchospasm from presumed allergy (NAC therapy stopped).
 - Double-blind randomized placebo-controlled trial delivering 150 mg/kg/day NAC intravenously over 24 hours for 1-7 days in children mean age 3.7 years (25%-75% 0.8-10.5 years) with non-acetaminophen-induced acute liver failure.¹⁹ No adverse events associated with NAC treatment were reported.
- b) Duration:

- **First seven days (168 hours +/-6 hours) after KP (post-operative day 0-7).** NAC was used post-operatively in numerous studies including:
 - Double-blind randomized placebo-controlled trial delivering 432 mg/kg/day NAC intravenously during abdominal aortic aneurysm repair and 288 mg/kg/day NAC intravenously for 24 hours post-operatively in adults age 72±11 years.³² No adverse events associated with NAC treatment were reported.
 - Double-blind randomized placebo-controlled trial delivering 600 mg oral NAC the day before coronary artery bypass grafting surgery requiring cardiopulmonary bypass, followed by 150 mg/kg NAC intravenous over 15 minutes immediately before surgery, followed by 300 mg/kg/day NAC intravenously for 24 hours post-operatively in adults age 59.8±7.8 years.³³ No adverse events associated with NAC treatment were reported.
 - Double-blind randomized placebo-controlled trial delivering a total of 300 mg/kg/day NAC intravenously for 24 hours in adults undergoing cardiac surgery with cardiopulmonary bypass age 68.9±9.7 years (150 mg/kg for 15 minutes, followed by 50 mg/kg for 4 hours, followed by 100 mg/kg for 20 hrs).³⁴ No adverse events associated with NAC treatment were reported.
- c) Formulation:
 - Dilute of 200 mg/ml stock solution (2600 mOsm) stock to 10 mg/ml with 5% dextrose in water (382 mOsm), per standard pharmacy protocol
 - Deliver 0.625 ml/kg/hour (equivalent to 6.25 mg/kg/hour or 150 mg/kg/day)
 - Resulting final rate (>1 ml/hour, depending on weight) is sufficient to keep intravenous line open

	Pre-	Days	s Post	t-KP	Weeks Post-KP							Months of Life		
	KPa	3 ^{b,c}	7	10	2	4	8	12	18	24	12	18	24	
Demographic data														
TSBAs														
Bc														
AST/ALT														
GGT														
Albumin														
Sodium														
Total Bilirubin														
Platelets														
INR														
25-hydroxy Vitamin D														
Vitamin A														
Vitamin E														
Weight														
Sentinel/Adverse events														

v. Observations for this study, performed as part of standard clinical care

^aDrawn within seven days of KP

^bIf laboratory adverse event occurs (see Table 4), will perform an additional measurement 5 days post-KP ^cAny "days post-KP labs (3,7,10) drawn outside of the outlined visit point will not be considered a deviation if +/- 2 days. For "weeks post-KP" labs (2,4,8,12,18,24) +/- 7 days window and "months of life" labs (12,18,24) +/-2 weeks window.

- a) Primary outcomes:
 - Any normal TSBA (0-10 umol/L) in the first 24 weeks after KP
- b) Secondary outcomes:
 - Trajectory of TSBAs changes over study period
 - Trajectory of Bc changes over study period (drawn as part of liver panel)
 - Trajectory of AST and ALT changes over study period (drawn as part of liver panel)
 - Trajectory of GGT changes over study period (drawn as part of liver panel)
 - Trajectory of albumin changes over study period (drawn as part of liver panel)

- Trajectory of sodium changes over study period (drawn as part of chemistry panel)
- Trajectory of Total Bilirubin changes over study period
- Trajectory of platelets changes over study period (drawn as part of complete blood count)
- Trajectory of INR changes over study period
- Trajectory of 25-hydroxy Vitamin D concentrations over study period and correlate with fat-soluble vitamin supplementation
- Trajectory of Vitamin A concentrations over study period and correlate with fat-soluble vitamin supplementation
- Trajectory of Vitamin E concentrations over study period and correlate with fat-soluble vitamin supplementation
- Trajectory of weight z-score changes over study period (to detect fluid overload during the infusion period and growth effects at later times)
- Sentinel events during the study period related to liver disease, such as cholangitis, ascites, liver transplant listing, liver transplant, and/or death (see Data and Safety Monitoring Plan (DSMP) in Appendix)
- Adverse events in the first 28 days after KP possibly related to NAC, including rash, urticaria, pruritus, tachycardia, hypotension, vomiting, edema, anaphylaxis, and intravenous line issues (see DSMP in Appendix)
- **vi. Dose Modifications** Rules for modifying NAC infusion are as follows, based in part on prior recommendations for NAC therapy in acetaminophen toxicity (also see DSMP in Appendix):³⁵
 - a) Flushing alone, without pruritus, urticaria, or other serious signs
 - No intervention
 - Continue infusion, unless more severe signs develop
 - b) Urticaria
 - Stop infusion
 - Treat immediately with intravenous diphenhydramine (1.25 mg/kg/dose)
 - Restart infusion if symptoms resolve within 1 hour
 - c) Angioedema, hypotension, wheezing
 - Stop infusion
 - Treat with intramuscular epinephrine (0.01 mg/kg/dose), intravenous diphenhydramine (1.25 mg/kg/dose), intravenous glucocorticoid (1 mg/kg/dose), and/or inhaled albuterol, at the discretion of the clinical team
 - Do not restart infusion
 - Continue to follow patients for first two years of life, per study protocol
 - d) Elevation of ALT >700 U/L above baseline, Bc 3x above baseline, TB 3x above baseline, and/or Bc >5 mg/dL above baseline
 - Stop infusion
 - Do not restart infusion
 - Follow patients clinically until elevated ALT/Bc stabilizes/resolves
 - Evaluate for drug-induced liver injury if deemed appropriate by the clinical team, based on FDA recommendations (https://www.fda.gov/downloads/Drugs/.../guidances/UCM174090.pdf)
 - e) If a severe adverse event related to or possibly related to the study drug (see DSMP in Appendix for definition) occurs during the first 7 days of the trial, i.e., during NAC infusion, the infusion will be paused, and an emergency Data Safety Monitoring Board (DSMB) meeting will be convened. If the DSMB deems that causality is unrelated to NAC use, then the trial can be continued.

vii. Concurrent Treatments

a) Standard therapies: All standard therapies will be given during the study period, including ursodeoxycholic acid (20 mg/kg/day), fat-soluble vitamins (AquADEK, 1 ml once or twice daily), and up to one year of post-KP antibiotics (trimethoprim/sulfamethoxazole 5 mg/kg/day). In infants found

to have low Vitamin A levels (<20 mcg/dL), intramuscular Vitamin A injections of 50,000 IU will be given two days before KP and 28 days after KP. Steroids will not be used as standard post-KP care.

b) Experimental therapies: No other investigational therapies will be given during the study period.

viii. Removal of Patients from Study

- a) Parents may voluntarily exclude their infant from the study at any time
- b) The investigators may remove a patient if the study team decides that continuation is not in the best interest of the participant of the study (i.e., patient receives another experimental therapy during the two-year study period that will confound the results).

E. Data Collection

- i. Clinical Data All clinical data (laboratory results, weights, occurrence of sentinel events) will be stored in the patient's electronic medical record. In addition, a comprehensive study form containing all data for each subject will be updated as new results become available.
- ii. Adverse Events All adverse events (observed by the study team, reported by parents, and/or detected by laboratory findings) will be recorded in the patient's medical record as well as separate form specifically for the study. The form will be submitted to the DSMB following a pre-determined schedule (see DSMP in Appendix).

F. Statistical Considerations

i. Overview

This is a Phase 2 clinical trial using the two-stage "minimax" design described by Simon.²⁹ As a Phase 2 trial, the trial's objective is to determine whether NAC

has sufficient biological activity as adjunctive therapy for BA to warrant further study. By choosing the two-stage "minimax" design, we gain two advantages: (i) early termination if the drug is not efficacious, and (ii) using historical controls and therefore an overall smaller sample size to test the hypothesis, i.e., no randomization or control arm. This study design only identifies large effects (response >20%). For BA this is appropriate, because the field is in need of a robust therapy that can substantially limit liver damage and delay/prevent need for liver transplantation.

Historical controls from the START clinical trial will be used for the primary outcome, as this is the only systematic examination of TSBAs after KP.⁴ In the START trial, subjects receiving a KP between 2005-2011 were enrolled and TSBAs drawn as many as eight times (pre-KP; 1, 2, 3, and 6-months post-KP; and 12, 18, and 24 months post-KP). We will examine these results to determine the number of subjects with normal TSBAs after six months. We expect a maximum of 5% of subjects to have normalized TSBAs, based on a recent publication of correlating TSBAs from the START trial with fat-soluble vitamin levels (118 data points taken at 1, 3, or 6 months post-KP) (Figure).⁵

For secondary outcomes, results will be compared to previously published findings and results from our institution. For example, laboratory and clinical two-year outcomes for BA have been described previously, for all infants receiving KP and those with total bilirubin <2 mg/dL vs. \geq 2 mg/dL within 3 months of KP.^{3,36} In addition,

of the patients receiving a KP at our institution between 2007-2014, only 1/48 (2.1%) had a normal Bc recorded in the first two weeks post-KP.

One limitation of this approach is that using historical controls can lead to a type 1 error, because BA management has evolved over time. For example, newborn screening now allows for earlier diagnosis and treatment with the KPs. In addition, at our center intramuscular Vitamin A is now used to correct Vitamin A levels quickly, alongside the oral fat-soluble vitamin preparations used in the past. Finally, nutritional approaches have changed, including use of early parenteral nutrition immediately after KP. These changes may alter outcomes independent of intravenous NAC treatment.

ii. Sample-Size Calculations

Simon's two-stage "minimax" design will be used to calculate sample sizes for the primary outcome.²⁹ The null hypothesis will be tested against a one-sided alternative. Assuming a normalization rate of approximately 5% (see above), the null hypothesis is that the true response rate is 5% for normalization of TSBAs 24 weeks after KP. In the first stage, 12 patients will be accrued. If no patient normalizes TSBA within 24 weeks of KP, the study will be stopped. Otherwise, 4 additional patients will be accrued for a total of 16. The null hypothesis will be rejected if \geq 3 of 16 patients normalize TSBA within 24 weeks of KP. This design yields a type I error rate of 5% and power of 80% when the true response rate is 25%. Subjects that do not complete the 7 day NAC infusion after the Kasai operation and 24 weeks of follow up may be replaced at the discretion of the PI/IND Sponsor.

G. Ethical Issues

i. Informed Consent

Participants will only be enrolled after their parent(s)/guardian(s) understand the nature and objectives of the trial, as well as the attendant risks and possible discomforts. All families will be given a consent form describing NAC and possible side-effects (see Consent in appendix).

ii. Children as Research Subjects

NAC may benefit patients with BA by improving bile flow after KP. This study does have risks. Intravenous NAC has been studied extensively in pediatric populations. NAC side effects include anaphylaxis reactions, generalized urticaria, hives, rash, stomatitis, rhinorrhea, and vomiting. These side effects are most often reported at the beginning of NAC infusion for acetaminophen toxicity, when higher doses than used in this study are administered.

This study also involves an intravenous line for NAC administration and blood draws. The intravenous line is routinely placed pre-operatively to deliver fluids when enteral feeds must stop. The same intravenous line will be used for NAC administration. The only instance in which an additional peripheral intravenous line will be placed is if intravenous access is lost during the seven-day period of NAC treatment. All blood draws for this study will be part of routine clinical care, and would be performed independent of participation in this trial.

H. Pharmaceutical Information

- i. Formulation Stock 200 mg/ml (2600 mOsm) packaged as Acetadote, dispensed after diluting in 5% dextrose to 10 mg/ml (382 mOsm) per standard pharmacy protocol (no new formulations used for this protocol).
- **ii. Storage** Stock stored at room temperature. Following reconstitution, stable for 24 hours at room temperature.
- **iii.** Administration Days 0-7 after KP: Intravenously at 0.625 ml/kg/hour, initially through intravenous line already present for routine clinical care and additional intravenous line if needed.

iv. Toxicities

NAC has been well studied at higher doses used in this study, for treatment of acetaminophen-induced liver toxicity. In adults, the most common side effects were cutaneous hypersensitivity reactions, including rash and/or urticaria on the face, neck, or arms.³⁷ These symptoms resolved with antihistamine use, without requiring treatment changes in most cases. Respiratory hypersensitivity reactions have also been reported, including one case of bronchospasm in a patients with asthma resulting in death.¹⁵ In a pediatric center, NAC treatment for acetaminophen-induced liver toxicity was associated with adverse events in 46 of 89 patients. Adverse events were present in 40 of the 72 subjects receiving oral NAC, and included vomiting (n=29), nausea alone (n=10), and abdominal pain (n=2). Adverse events were present in six of the 17 subjects receiving intravenous NAC, and included vomiting (n=2), nausea alone (n=2), and rash (n=2).³⁸ No serious adverse events were recorded.

NAC is well-tolerated post-operatively after surgeries not requiring or requiring cardiopulmonary bypass.^{32–34} Previous in vitro results have suggested that NAC may impair platelet aggregation and coagulation parameters. One human study delivered 150 mg/kg NAC intravenously to patients undergoing abdominal aortic aneurysm repair followed by 150 mg/kg NAC intravenously for 24 hours.³⁹ All patients in this study received heparin during the operation and protamine post-operatively. Compared to controls, intravenous NAC treatment was associated with decreased prothrombin time Quick values, prolonged coagulation times in thromboelastometry tracings, and impaired platelet aggregation. However, NAC did not affect blood loss. While the clinical significance of these findings is unclear, the authors caution against NAC use in patients with pre-existing coagulopathies (patients with INR > 1.3 unresponsive to parenteral Vitamin K are excluded from this study).

Two potentially more serious events have been associated with NAC treatment. The first is severe hyponatremia leading to seizures, after excessive free water was given during intravenous NAC administration in infants.⁴⁰ This occurred partly because NAC therapy for acetaminophen toxicity requires three dose changes in the first five hours, with different NAC concentrations and dilution regimens. To minimize the chances of this occurring, special neonatal dilution instructions are included in the product insert and have been approved by the Food and Drug Administration.¹⁵ The single dilution strategy used in this protocol conforms to these recommendations.

Another potentially serious event that has been reported with oral NAC is paradoxical respiratory adverse drug reactions (ADRs).⁴¹ These events are described as worsening of respiratory disease in patients taking oral overthe-counter NAC (approximately 20-30 mg/kg/day children ages 1 month to 2 years) as a mucolytic agent in the setting of bronchiolitis or pneumonia. NAC is proposed to increase bronchial mucus flow which can overwhelm an infant's ability to spontaneously clear secretions. Fifty-nine cases were identified over a 20 year period in European country. However, in studies of intravenous doses similar to the dose used in this investigation, no paradoxical respiratory ADRs were reported.

A summary of the side-effect profile of intravenous NAC listed on formularies is as follows:

Cardiovascular:	Edema, flushing, tachycardia							
Dermatologic:	Rash, pruritus, urticaria							
Gastrointestinal:	√ausea, vomiting							
Immunologic:	Autoimmune disease							
Miscellaneous:	Anaphylactoid reaction							
Respiratory:	Pharyngitis, rhinorrhea, rhonchi, throat tightness							
Rare but important or life-threatening:	Anaphylaxis, angioedema, bronchospasm, chest tightness, cough, dizziness, dyspnea, hypotension, respiratory distress, stridor, wheezing							

N-Acetylcysteine in BA **I. References**

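### The renal exclusion C.ii(d) pairs a limit per 1.73 m² with the same number in plain mL/min, and the two contradict each other in an infant trial

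*Combined protocol and SAP*

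**What the plan says.** Section C.ii, exclusion (d), has two limbs. The first is "Renal impairment, as defined by having an eGFR < 60 mL/min/1.73m²". The second follows directly: "or creatinine clearance < 60 mL/min". A web link to a paediatric calculator page comes after both limbs; its address ends in "glomerular-filtration-rate-calculators/children-conventional-units". No wording says that the link changes the units printed before it.

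The population is set by inclusion (a), "Age less than or equal to 90 days at time of KP", and again in section C.vi, "This trial will only enroll infants ≤90 days old". Planned enrolment (C.iii) is 12 to 16 subjects.

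Nothing elsewhere in the protocol or its appendices defines creatinine clearance as normalised to body surface, or says that one limb prevails over the other.

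**The concern.** An absolute clearance in mL/min scales with body size, whereas a value per 1.73 m² has body size taken out. Putting the same number, 60, on both scales gives one limit only for a patient whose body surface is 1.73 m². This trial takes infants of 90 days or younger. Because the limbs are joined by 'or', falling under either one excludes on the plain reading.

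What is at stake is whether the criterion can be applied and checked as printed. Under the literal wording an enrolled infant could appear to meet an exclusion, and the protocol offers no text to settle the question. Section F.i compares the results of this single arm with historical controls, so who was eligible should be reproducible from the written criteria.

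**Working it through.** The plan derives no figure here, so there is nothing to reproduce first. The check is a unit conversion.

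**Inputs from the documents**
- First limb: 60 mL/min/1.73 m² (C.ii(d)).
- Second limb: 60 mL/min (C.ii(d)).
- Age at most 90 days (C.i(a), C.vi).
- Body size: the only hint is in section D.iv(c), "Resulting final rate (>1 ml/hour, depending on weight) is sufficient to keep intravenous line open". At 0.625 ml/kg/hour, a rate above 1 ml/hour implies a weight above 1 / 0.625 = 1.6 kg. No upper weight and no body surface area (BSA) is given.

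**Assumptions, not in the documents**
- Infant BSA of 0.15 to 0.40 m². This covers roughly 2 to 8 kg by the Mosteller formula, BSA = √(kg × cm / 3600), with assumed lengths. For example, 8 kg and 66 cm give √(8 × 66 / 3600) = 0.383 m².
- Infant clearance of at most 200 mL/min/1.73 m², taken as a deliberately high ceiling.

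**Step 1. Where the limits agree.** Absolute clearance = indexed value × BSA / 1.73. Setting both values to 60 gives BSA = 1.73 m². At any smaller BSA, an indexed value below 60 forces an absolute value below 60. So, if both limbs describe the same filtration rate, everyone caught by the first limb is already caught by the second, and the first is redundant. This step needs no infant figures beyond a BSA below 1.73 m².

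**Step 2. Size of the mismatch.** The indexed equivalent of 60 mL/min is 60 × 1.73 / BSA = 103.8 / BSA. The absolute equivalent of the indexed limit is 60 × BSA / 1.73.

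| BSA (m²) | 60 mL/min expressed per 1.73 m² | Indexed 60 expressed in mL/min |
|---|---|---|
| 0.15 | 692 | 5.2 |
| 0.20 | 519 | 6.9 |
| 0.25 | 415 | 8.7 |
| 0.30 | 346 | 10.4 |
| 0.35 | 297 | 12.1 |
| 0.40 | 260 | 13.9 |

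The ratio of the two limits is 1.73 / BSA: 1.73 / 0.40 = 4.3 at the large end and 1.73 / 0.15 = 11.5 at the small end. An infant of 1.6 kg (assumed length 40 cm) has a BSA of about 0.133 m², just below the range, and there the mismatch is larger still (778 mL/min/1.73 m²).

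**Step 3. Can any candidate clear the second limb?** Absolute clearance at an assumed indexed value:

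| Indexed value | at BSA 0.15 m² | at BSA 0.40 m² |
|---|---|---|
| 120 | 120 × 0.15 / 1.73 = 10.4 mL/min | 120 × 0.40 / 1.73 = 27.7 mL/min |
| 200 | 200 × 0.15 / 1.73 = 17.3 mL/min | 200 × 0.40 / 1.73 = 46.2 mL/min |

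All four values are below 60. To reach 60 mL/min at an indexed value of 200, BSA would have to be at least 60 × 1.73 / 200 = 0.519 m², which is outside the assumed range.

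**Step 4. Link to the design.** The two-stage rule in section F.ii depends only on the numbers of patients and of responders and on the assumed response rates. The renal criterion does not enter it.

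**The case against.** The strongest reply is that this is a dropped unit suffix and nothing more. The criterion repeats the number 60, presents both limbs as a definition of one condition, and is followed by a link to paediatric GFR calculators. A literal reading that leaves no eligible infant cannot be what a protocol planning 12 to 16 subjects intends, so in effect only one reading remains. The second limb may also never come into play. Section D.i allows no testing beyond routine care, and neither the observation table in D.v nor the sample Data CRF has a row for creatinine or creatinine clearance. The 'or' could simply mean whichever measure is on file.

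Most of this stands. A normalised value is the probable intent, and that is why the point is minor. It does not make the printed criterion usable. The linked page cannot be seen here and no text gives it precedence. If 'or' means whichever measure is available, the same infant could be eligible by one measure and excluded by the other.

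Two stronger readings are tempting. A reader might infer that the units alone prove every infant is excluded. They do not: the printed units show that the limits conflict and that the un-indexed one is stricter, but universal exclusion also needs the BSA and clearance assumptions stated above. A reader might also infer that staff have been ignoring half of the criterion, that enrolled infants were in fact ineligible, or that accrual was blocked. The documents contain no screening or enrolment data and do not report how the criterion was applied, so they support none of these. For the same reason they do not show that enrolment was unaffected.

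**Conclusion.** Wrong as written, minor severity. That the two limbs of C.ii(d) are on different scales, and agree only at a BSA of 1.73 m², is plain from the text and certain. The size of the conflict, a factor of about 4 to 12, rests on the assumed BSA range. The statement that, read literally, the criterion would exclude every candidate rests on that range together with the assumed clearance ceiling; it holds throughout the ranges shown. The consequence is an eligibility criterion that cannot be applied or audited as printed. There is no effect on the stopping rule, the type I error or the power.

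**What to change.** The sponsor should reconcile the two limbs of C.ii(d) so that they are on one scale and cannot contradict each other. The clinical team should set the limit; no cut-off is proposed here, nor which limb should stand. It would help to state in the same line how the value is obtained and what role the linked calculator has. The cost is a one-line amendment, with no change to the sample size, the endpoint or the analysis.
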